### **Sunitinib in Pancreatic Neuroendocrine Tumours**

In pNET, there is a high expression of VEGF and VEGFR2-3, PDGFR alpha and beta, cKIT and EGFR, and hypoxia are a key event in the regulation of tumour angiogenesis. This constitutes a strong rationale when it comes to developing anti-angiogenic drugs for these tumours. In clinical studies, the activity of sunitinib on NET was first demonstrated in a phase I study where the 3 enrolled NET patients, all of whom had been previously treated, showed reduced tumour lesions to varying degrees, being exceptional in one patient with a higher partial response (21 weeks) and two long-lasting minor responses (13). Thereafter, a multicenter, phase II study was conducted in patients with carcinoid tumours and pNET (14). Results from the 66 pNET

patients showed an objective response rate of 16.7% and a stable disease rate of 68%. The time to progression and overall survival at one year was 7.7 months and 81.1%, respectively. To definitively confirm this benefit, a phase III study versus placebo was developed, in which 171 patients of the 340 initially estimated were finally randomised against independent data monitoring (15). The benefit in terms of PFS was 11.4 months for the sunitinib arm at a dose of 37.5 mg/day versus 5.5 months for the placebo arm (HR 0.42;  $p < 0.001$ ). Efficacy data on patients in routine clinical practice treated with sunitinib were consistent with those obtained on selected populations in clinical trials (16).

**Figure 1 PFS results of the phase III study of sunitinib vs. placebo in pNET patients.**

## TH-302 (Preclinical and Clinical Development in Solid Tumours)

### • Introduction

(1-methyl-2-nitro-1H-imidazole-5-yl) methyl N, N'-bis (2-bromoethyl) diamidophosphate (also known as TH-302) is a nitroimidazole-triggered prodrug of a brominated version of isophosphoramidate mustard (Br-IPM) (17). TH-302 is able to diffuse into hypoxic tissues without activation by NADP (H) quinone oxidoreductase (DT-diaphorase). It is preferentially activated under severe hypoxic conditions that are unlikely to be present in healthy tissue but in solid tumours (18).

The molecule TH-302 is activated by a process that involves a one electron reduction at the 2-nitroimidazole site of the prodrug, mediated by ubiquitous cellular reductases such as the NADPH-cytochrome P450, to generate a radical anion prodrug (RP). In the presence of oxygen (normoxia) the radical anion prodrug reacts rapidly with oxygen to generate the original prodrug and superoxide (SO). In these situations, TH-302 is relatively inert, remaining intact as a prodrug. However, under hypoxic conditions, (<0.5% O2), the radical anion prodrug can either fragment directly or undergo further reduction at the nitroimidazole site of the prodrug, causing Br-IPM to be released (Figure 2). Br-IPM can then act as a DNA alkylating agent and

form DNA crosslinks, causing damage through the presence of  $\gamma$ H2AX. Br-IPM can diffuse through normoxic tissues and act as a cytotoxic agent in these regions. Previously, other alkylating mustards such as ifosfamide or cyclophosphamide had already demonstrated activity in many tumours.

Tumours often contain highly hypoxic regions that are known to be resistant to chemotherapy and radiotherapy. These regions develop due to the creation of irregular and aberrant blood vessels that prevent adequate oxygenation and penetration of the majority of chemotherapy treatments, which act on highly proliferating cells adjacent to the blood vessels, but not on the relatively quiescent cells found in the hypoxic regions. For this reason, they are resistant to these regimens of cytostatic drugs (19). In contrast, the prodrug TH-302 is activated in conditions of severe hypoxia, and not in the majority of normal tissues with a similar structure (20). Recent preclinical findings support the hypothesis of the induction of hypoxia within the tumour developed by anti-angiogenic drugs, which could constitute a synergistic effect with TH-302.

The molecular formula of TH-302 is  $C_9H_{16}Br_2N_5O_4P$  and the molecular mass is 449 g/mol.

**Figure 2 TH-302 activation pathway diagram**

[figure not shown]

Figure obtained from Meng, F., et al. Molecular and cellular pharmacology of the hypoxia-activated prodrug TH-302. *Mol Cancer Ther.* 2012;11:740–51

#### • Preclinical Data

In preclinical investigations, TH-302 as monotherapy or in combination with numerous cytotoxic drugs has shown broad activity in murine models (21). In particular, TH-302 has shown consistent activity in cell lines from neural crest derived tumours such as melanoma and glioblastoma/astrocytoma (TH-302 Investigator's Brochure).

TH-302 is very active in vitro, as demonstrated in proliferation studies of H460 lung carcinoma cells (22), where TH-302 activity is related to dose-exposure and oxygen dependence, which practically achieves linearity (23). This activity is also observed in H69 small-cell lung cancer cells (SCLC), B16-F10 melanoma, SKMEL-5 melanoma, HT-29 colon cancer, HCT116 colon cancer, MES-SA uterine cancer, DX5 uterine cancer, ACHN renal cancer and PC-3 prostate cancer in anoxic conditions ( $CI_{50}$  from 0.1 to 10  $\mu$ M) and weakly cytotoxic in the presence of air ( $CI_{50} > 80 \mu$ M). Consistent results are obtained in clonogenic models.

In vivo studies demonstrate activity both as monotherapy and in combination with other cytostatic drugs (cisplatin, paclitaxel or 5-fluorouracil) (22).

The effect of TH-302 has been studied in many murine xenograft models (H82 small-cell lung cancer, H460 and Calu-6 non-small cell lung cancer, A375 and Stew2 melanoma, 786-0 renal

cell and PLC/PRF/5, Hs766t and BxPC-3 pancreatic cancer). The cytotoxic activity of TH-302 increases in vivo in hypoxic conditions, as shown by excision methods and tumour growth models. Acute (single dose) or chronic (for 2 weeks) treatment with TH-302 demonstrates selective reduction in tumour volume of the hypoxic regions in xenograft models, with their corresponding increase in necrotic compartments (20). TH-302 achieves a significantly greater benefit in combination with chemotherapy, and even the complete eradication of some tumours, including metastatic ones (24).

With regard to the combination with anti-angiogenic drugs, the rationale starts from the knowledge of hypoxia induced by these agents that, in tumour progression, provide a more aggressive phenotype. The study of murine xenograft models in human 786-O renal cell carcinoma, melanoma A375, H460 non-small cell lung cancer and hepatocellular carcinoma PLC/PRF/5, investigated the synergistic activity of TH-302 in combination with sunitinib or sorafenib (25). Both anti-angiogenic drugs increased hypoxia detected in the tumour tissue, and were time and dose-dependent. In the 786-O renal cell model, the activity of sunitinib (40 mg/kg) increased when combined with TH-302 (50 mg/kg) in terms of tumour growth control, from 38% to 75%. In addition, no significant weight loss was identified when combining anti-angiogenic drugs with TH-302, which is an indicator of toxicity. In conclusion, the synergism reached in terms of the anti-tumour efficacy of the combination of sunitinib or sorafenib with TH-302 by selective action on hypoxic tissue induced by anti-angiogenic drugs, forms the basis for the future clinical development of this combination.

## 1.2. STUDY OBJECTIVES

### 1.2.1. PRIMARY OBJECTIVE

Objective response rate (ORR).

### 1.2.2. SECONDARY OBJECTIVES

Secondary endpoints are:

[figure not shown]
- Progression-free survival (PFS)
- Time to progression (TTP)
- Response duration (RD)
- Overall survival (OS)
- Safety
- Serological and tumour tissue biomarkers

### 1.2.3. SAFETY OBJECTIVE

To determine the safety of TH-302 in combination with sunitinib.

### 1.3. STUDY FLOWCHART

Figure 3 Trial Schema

### 1.4. STUDY POPULATION

#### 1.4.1. Selection criteria

Patients with a well- or moderately-differentiated metastatic pancreatic neuroendocrine tumour (pNET) (grade 1-2 of histological differentiation and Ki67  $\leq$  20%) who are naive to systemic treatment, with the exception of somatostatin analogues, will be eligible for the trial if they meet all the inclusion criteria and none of the exclusion criteria, as described below.

#### 1.4.1.1 Inclusion criteria

For inclusion in the study subjects should fulfil the following criteria:

1. Age  $\geq$  18 years capable of giving informed consent.
2. ECOG performance status (Eastern Cooperative Oncology Group) 0 or 1
3. Pancreatic neuroendocrine tumours (pNET) diagnosed histologically with a Ki67  $\leq$  20% (well- or moderately-differentiated tumours).
4. Evidence of unresectable or metastatic disease. Locally advanced disease must not be amendable to surgical resection or radiation therapy with curative intent.
5. Prior systemic therapy is not permitted. Patients may be treated with somatostatin analogues prior to or during the trial. Concomitant or prior interferon (IFN) treatment is not permitted.
6. Tumour progression documented by CT scan, MRI or octreoscan within 12 months prior to the baseline visit.

7. Measurable disease by RECIST 1.1 criteria. Measurable lesions that have been previously radiated will not be considered target lesions unless increase in size has been observed following completion of radiation therapy.
8. The patient must be able to consume the medication orally.
9. Life expectancy more than 12 weeks.
10. The required laboratory values corresponding to adequate organ function and bone marrow are as follows.
  - Aspartate aminotransferase (AST) and alanine aminotransferase (ALT)  $\leq 2.5 \times$  upper limit of normal (ULN), or AST and ALT  $\leq 5 \times$  ULN if liver function abnormalities are secondary to underlying malignancy.
  - Total serum bilirubin  $\leq 1.5 \times$  ULN
  - Serum albumin  $\geq 3.0$  g/dl
  - Absolute neutrophil count  $\geq 1500/\mu\text{l}$ .
  - Platelets  $\geq 100,000/\mu\text{l}$
  - Haemoglobin  $\geq 5.6$  mmol/l (9 g/dl)
  - Creatinine clearance  $> 40$  ml/min (Cockcroft and Gault Formula)
11. Suitable cardiac function:
  - 12-lead ECG with no pathological findings (non-clinically significant abnormalities are permitted)
  - Normal echocardiogram/MUGA normal (LVEF  $\geq 50\%$ )
12. Informed consent with date and signature indicating that the patient (or legal representative) has been informed of all study aspects prior to enrolment.
13. The patient must be able to comply with the required study visits, treatment, laboratory tests and other study procedures.

#### **1.4.1.2 Exclusion criteria**

Patients should not enter the study if any of the following exclusion criteria are fulfilled:

Patients must NOT meet any of the following exclusion criteria:

1. Previous treatments with chemotherapy, anti-VEGF monoclonal antibodies, tyrosine kinase inhibitors (TKI), mTOR inhibitors or interferon (IFN) administered for advanced disease.
2. Prior treatment with another hypoxia-activated drug under clinical trial.
3. Major surgery, radiotherapy or systemic therapy within 4 weeks prior to study enrolment, except palliative radiotherapy for non-target metastatic lesions.
4. Prior high-dose chemotherapy requiring haematopoietic stem cell rescue.
5. Immunosuppressive drugs such as cyclosporine, tacrolimus, azathioprine, or long-term corticosteroids taken concurrently or within 3 months prior to study enrolment.

6. Treatment, within 7 days prior to study enrolment, with known strong CYP3A4 inhibitors or inducers, or drugs that prolong the QT interval.
7. Prior radiation therapy to > 25% of the bone marrow.
8. Treatment within another clinical trial.
9. Uncontrolled brain metastatic disease, spinal cord compression, carcinomatous meningitis or leptomeningeal disease. Patients should have completed surgery or radiation therapy for existing brain lesions, should not have documented increase in size of said lesions over the three months prior to the first study treatment dose, and should be asymptomatic.
10. Diagnosis of any second malignancy within the last 3 years, except for adequately treated basal cell or squamous cell skin cancer, or carcinoma in situ of the cervix.
11. Clinically significant cardio/cerebrovascular disease within 12 months prior to treatment initiation, including:
  - Myocardial infarction
  - Severe/unstable angina
  - Coronary/peripheral artery bypass graft
  - Congestive heart failure NYHA (New York Heart Association) Class III or IV, or patients with a history of congestive heart failure NYHA class III or IV, unless an echocardiogram or MUGA scan within 3 months prior to screening shows a left ventricular ejection fraction  $\geq 45\%$ .
  - Significant cardiac valvular heart disease.
  - Cerebrovascular accident including transient ischaemic attack.
  - Pulmonary thromboembolism.
12. Cardiac arrhythmias (NCI CTCAE version 4.0 grade  $\geq 2$ ), atrial fibrillation of any grade, or QTc interval > 450 msec for males or > 470 msec for females.
13. Hypertension that cannot be controlled despite optimal medical therapy (> 150/100 mmHg)
14. Chronic obstructive pulmonary disease (COPD) or any lung disease accompanied by hypoxaemia or oxygen saturation < 90% after a 2-minute walk.
15. Current treatment with therapeutic doses of acenocoumarol (administration of low doses of acenocoumarol up to 2 mg/24 h for deep vein thrombosis prophylaxis is permitted).
16. Known human immunodeficiency virus (HIV) infection.

17. Pregnant or breast-feeding. All female patients of childbearing age must have a negative pregnancy test (blood or urine) prior to study enrolment.
18. Prior allergic reaction to ingredients structurally similar to TH-302 or sunitinib or to any of the drugs' excipients.
19. Non-healing wound, fistulae, active stomach ulcer or bone fractures.
20. Any condition (medical or psychiatric) or reason that, in the opinion of the investigator, would interfere with the patient's ability to participate in the clinical trial, by placing the patient at excessive risk or by complicating the interpretation of the safety data, therefore being unsuitable for enrolment in the study.

## 1.5. STATISTICAL METHODS AND SAMPLE SIZE DETERMINATION

### 1.5.1. DESCRIPTION OF ANALYSIS SETS

#### 1.5.1.1 Total analysis population

All safety and efficacy analyses will be based in the total analysis population. Any patient fulfilling all the inclusion criteria and none of the exclusion criteria will be included the total analysis population.

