5. STUDY DESCRIPTION

5.1. Design

This is a prospective, non-randomised, open-label, single-arm, phase II study that will assess the efficacy and safety of TH-302 plus sunitinib in patients with well- and moderately-differentiated metastatic pancreatic neuroendocrine tumours (pNET) who are naïve to systemic treatment other than somatostatin analogues. The study will include a serological biomarker analysis to investigate its clinically beneficial prognostic and predictive role.

The study will be conducted at 10 Spanish university sites belonging to the Spanish Task Force Group for Neuroendocrine Tumours (GETNE) network. GETNE will act as the study sponsor.

Once the patient has signed the informed consent form, he/she should be registered in the study, regardless of whether he/she meets the eligibility criteria, using the electronic data collection platform provided for the trial, at the following web address:

[REDACTED]

In the event that the patient meets all of the inclusion criteria and none of the exclusion criteria, an enrolment confirmation email will be sent with the corresponding patient number. The trial treatment may only be initiated once this confirmation has been received.

If any problems are detected with the tool during the enrolment process, or if the confirmation email is not received, please contact as soon as possible:

Marketing Farmacéutico & Investigación Clínica [Pharmaceutical Marketing & Clinical Research]

[REDACTED]

For more information concerning the enrolment procedure, please refer to the enrolment procedure available in the site's investigator files.

The tumour sample must be found and sent to [REDACTED] to perform the determinations detailed in this protocol. In addition, for patients who give their consent for the translational sub-study, blood samples (peripheral blood) must be collected prior to administration of the study medication and within the time limits defined in this protocol. These must be processed as laid out in section 8.1.

[figure not shown]
For more information about the shipment of the biological samples, please refer to the biological sample shipment procedure available in the site's investigator files.

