11. STUDY PROCEDURES

11.1. *Schedule of Assessments*

See Annex I.

11.2. *Baseline Visit (Days -28 to -1)*

At this visit the patient should be informed about all aspects of the study, including visits and tests to be performed. The patient will be asked to sign and date the informed consent form prior to performing any study procedure.

The informed consent form must be signed within 4 weeks before the start of the study medication. The original signed and dated informed consent form must be stored by the investigator in the patient's medical record and the patient must be provided with a copy.

The investigator will assess and confirm the eligibility of each patient, and all inclusion criteria must be met, but none of the exclusion criteria.

All the results of the tests undertaken during screening must be available before deciding whether a patient is eligible.

The specific baseline visit procedures envisaged by the protocol are as follows and must be performed within 28 days of initiating study treatment, or, failing that, screening must be repeated.

- Medical history.
- 12-lead ECG.
- Vital signs (blood pressure, heart rate, temperature, height and weight).
- A full physical examination.
- Complete blood test (See schedule of assessments, Annex I).
- NET markers (chromogranin A, enolase 1 and others depending on the tumour type).
- Urinalysis.
- Performance Status (ECOG Performance Status) (Annex 3).
- Concomitant medication.
- Echocardiogram/MUGA.
- Thoracic, abdominal, and pelvic CT scan (bone scan).
- Extraction of peripheral blood sample (biomarker analysis in blood).
- Tumour block for diagnosis of well- or moderately differentiated neuroendocrine tumour for biomarker analysis.

Patients should start the study treatment within two working days following the baseline visit.

11.3 Day 1 visit (may occur on the same day as the baseline visit if all baseline visit test results are available).

- Confirm that all the screening period and baseline visit procedures have been carried out.
- Confirm that the patient meets the inclusion criteria and none of the exclusion criteria.
- Instruct the patient regarding the administration of the study medication and provide the study medication for a complete cycle, i.e., 28 days.

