#### 2.1.2. Evaluable patients

Following protocol indications it was analysed which patients could be included in the analysis:

General inclusion criteria:

- Patients over 18 years with performance status ECOG 0 or 1.
- Obtaining informed consent in writing and signed.
- Pancreatic neuroendocrine tumours (pNET) diagnosed histologically with a Ki67 ≤ 20% (well- or moderately-differentiated tumours).
- Evidence of unresectable or metastatic disease. Locally advanced disease must not be amendable to surgical resection or radiation therapy with curative intent.
- Prior systemic therapy is not permitted. Patients may be treated with somatostatin analogues prior to or during the trial. Concomitant or prior interferon (IFN) treatment is not permitted.
- Adequate hematologic, hepatic, renal and cardiac function

In the following table the number of non evaluable patients along with the reason why, will be reported.

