**Table 17. Analysis sets**

		N (%)
Total analysis population	Yes	
	No	
Reason excluded	Reason 1	
	Reason 2	
	....	

If any patient is excluded from the total analysis population, it will be listed below along with the reasons why:

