## 2.8. SAFETY ANALYSIS

Adverse events and serious adverse events, laboratory test results, physical examination findings and vital signs, and their changes from baseline will be summarized using descriptive statistics. Abnormal values will be flagged.

The total analysis population will be used for the safety analysis.

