**Table 34. Adverse events**

Adverse Events	Grade 1 N (%)	Grade 2 N (%)	Grade 3 N (%)	Grade 4 N (%)	Total N (%)
Hematologic					
Neutropenia					
Anaemia					
Thrombocytopenia					
Metabolic/Laboratory					
GGT ( $\gamma$ -Glutamyl transpeptidase)					
Alkaline phosphatase					
Lipase					
AST, SGOT (serum glutamic oxaloacetic transaminase)					
ALT, SGPT (serum glutamic pyruvic transaminase)					
Gastrointestinal					
Nausea					
Diarrhoea					
Abdominal pain					
Constipation					
Vomiting					
Heartburn/dyspepsia					
Mucositis					
Others					
Hypertension					
Fatigue (asthenia)					
Dry mouth/salivary gland (xerostomia)					
Headache					
Anorexia					
Vaginal bleeding					
Fistula					
Hypothyroidism					
Subclinical Hypotiroidism					
Neuropathy					
Hepatic toxicity					

GGT: Gamma glutamil transpeptidase; AST: Aspartate aminotransferase; ALT: Alanine transaminase.

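### All safety tables use a set defined by eligibility alone, so a dosed patient later found ineligible drops out of the adverse-event rates

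*SAP*

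**What the plan says.** SAP 1.5.1.1 names one analysis set and gives it every analysis: "All safety and efficacy analyses will be based in the total analysis population". It defines membership by eligibility: "Any patient fulfilling all the inclusion criteria and none of the exclusion criteria will be included the total analysis population". Receipt of study drug is not mentioned. SAP 2.6 repeats both statements, and SAP 2.8 applies the set to toxicity by name: "The total analysis population will be used for the safety analysis". The output concerned is "Table 34. Adverse events".

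The SAP expects some patients to fall outside the set. SAP 2.1.2 says: "In the following table the number of non evaluable patients along with the reason why, will be reported". SAP 2.6 adds: "If any patient is excluded from the total analysis population, it will be listed below along with the reasons why". The resulting Table 18 has three columns: patient code, set membership and reason for exclusion.

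The protocol places a check before dosing. Section 5.1 says of the enrolment confirmation: "The trial treatment may only be initiated once this confirmation has been received". Section 11.2 says: "All the results of the tests undertaken during screening must be available before deciding whether a patient is eligible". Section 10.2.2 requires all adverse events to be recorded for all patients, whether or not they are related to the drug.

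**The concern.** Toxicity rates should describe everyone exposed to the treatment. A set defined by eligibility removes some exposed patients for a reason unrelated to whether they took the drug. That reason may be related to their risk, because many of the criteria are safety screens: organ function, ejection fraction, QTc interval, cardiovascular history, interacting drugs and uncontrolled hypertension.

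Protocol 1.12 names safety together with activity in the study's main purpose and lists it again as a secondary objective. With one arm and about 43 patients, one or two omissions can move a reported rate by a few percentage points, or remove a rare event from the table.

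**Working it through.** The plan states no figure on this point, so there is none to reproduce. The check is a reading of the texts followed by an illustration.

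**1. Does any text bring dosed but ineligible patients back into the safety tables?**

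- Protocol 9.1 and 10.2.1, and SAP 1.5.3 and 1.5.5.1, give time windows and types of safety data. They define no population.
- The condition of at least one dose appears only in the sample-size text (Protocol 5.4, SAP 1.5.4). There it qualifies eligible patients, so it narrows the eligible group and does not widen it to all treated patients.
- Tables 17 and 18 in SAP 2.6 show the number excluded and the reasons. They carry no toxicity data.

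No text does so. The events are collected under Protocol 10.2.2 but have no place in Table 34.

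**2. How far could a rate move?**

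Inputs:

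- 43 eligible and dosed patients (Protocol 5.4, SAP 1.5.4).
- *k* = 1 or 2 further patients who were dosed but ineligible. This is an assumption, as the documents give no count.
- 4 events among the 43. This is also an assumption, for illustration.

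Rate reported under the SAP: 4/43 = 9.3%.

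Rate among all dosed patients: (4 + *x*)/(43 + *k*), where *x* is the number of the *k* patients who had the event.

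| *k* | *x* | All dosed | Rate |
|---|---|---|---|
| 1 | 0 | 4/44 | 9.1% |
| 1 | 1 | 5/44 | 11.4% |
| 2 | 0 | 4/45 | 8.9% |
| 2 | 1 | 5/45 | 11.1% |
| 2 | 2 | 6/45 | 13.3% |

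The range is 8.9% to 13.3% against a reported 9.3%. For an event seen only in one excluded patient, the table shows 0/43 = 0%, where the all-dosed rate is 1/44 = 2.3%.

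**3. Does the result depend on what 43 means?**

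Suppose instead that 43 is the number of all dosed patients, 4 of whom had the event (9.3%), and that *k* of the 43 are excluded. The reported rate is then (4 − *k*)/(43 − *k*) if all the excluded patients had the event, and 4/(43 − *k*) if none did.

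- *k* = 1: 3/42 = 7.1% to 4/42 = 9.5%.
- *k* = 2: 2/41 = 4.9% to 4/41 = 9.8%.

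The endpoints change, but the shift is again at most a few points and can go either way.

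**4. The opposite gap.**

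The definition sets no dosing condition, so an eligible patient who never starts treatment stays in the safety denominator. The tabulated events run from treatment initiation (SAP 1.5.5.1), so such a patient adds to the denominator without contributing events. SAP Table 12 makes room for patients with zero sunitinib cycles. With two such patients, 4/43 (9.3%) becomes 4/45 (8.9%).

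**The case against.** The strongest reply is that the SAP does not say when eligibility is judged. Under Protocol 5.1 it is settled at enrolment, before treatment. If that decision is final, every properly dosed patient is in the set. The sample-size text also treats eligible and dosed patients as one group. The exclusion tables might then hold only screen failures, since Protocol 5.1 registers everyone who signs consent, and SAP Table 4 sets recruited against non-recruited patients.

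Part of this stands. The pre-dose check makes cases uncommon, and the table shells are ambiguous. But SAP 1.5.1.1 contains no enrolment-time rule: it asks whether the patient fulfils the criteria. SAP 2.1.1 counts patients who were screened but not recruited separately, so Tables 2, 17 and 18 can plausibly contain recruited patients. Source-data verification under Protocol 13.3 can also reveal ineligibility after dosing.

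A second reply is that nothing turns on the difference. The safety analysis is descriptive, there is no safety threshold or stopping boundary, and the exact 95% interval for 4/43 (2.6% to 22.1%) contains the whole illustrated range. This is correct and limits the weight of the point. It does not justify leaving exposed patients out: sampling uncertainty is a separate matter from whether the table counts the right people.

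**Conclusion.** The concern holds. The SAP assigns all safety analyses to a set defined by eligibility alone, and neither document supplies a treated population. If a dosed patient is found ineligible at analysis, following the SAP removes that patient from Table 34.

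In the illustration, one or two such patients put the all-dosed rate between 8.9% and 13.3% where the table reports 9.3%. The number of patients and the number of events are both assumed; the true number affected may be zero. The point should be fixed, but it does not threaten the trial: it touches neither the primary response objective nor the collection and reporting of events.

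**What to change.** In SAP 1.5.1, 2.6 and 2.8, define a safety population of all patients who received at least one dose of sunitinib or TH-302, regardless of eligibility, and use it for all safety tables, including Table 34. Naming either drug matters because sunitinib is given alone in the first week. The same definition removes never-dosed patients from the denominator.

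As a separate minor point, carry the at-least-one-dose condition from the sample-size text into the total analysis population used for response. A response table for all treated patients is optional.

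The cost is SAP wording. The events are already collected, so no new data are needed. Reported toxicity rates may move slightly in either direction.
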